#### 10.11.9.5. Sample Size Determination

Since Substudy A is descriptive in nature, the planned sample size for the study is not based on any statistical hypothesis testing.

Approximately 90 participants will be enrolled in each vaccine group; therefore, a total of approximately up to 450 participants may be enrolled into this substudy.

For safety outcomes in the study, Table 6 shows the probability of observing at least 1 AE for a given true event rate of a particular AE with 90 participants in each vaccine group.

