2.2. Study Objectives, Endpoints, and Estimands

Type	Objective	Endpoint	Estimand
Primary safety	To define the safety and tolerability profile of tIRVs in participants 18 through 64 years of age	
 Local reactions (pain at the injection site, redness, and swelling) Systemic events (fever, fatigue, headache, chills, vomiting, diarrhea, new or worsened muscle pain, and new or worsened joint pain) AEs SAEs MAEs NDCMCs 	
In participants receiving study intervention (safety population), the percentage of participants reporting:
 
 Local reactions for up to 7 days following vaccination Systemic events for up to 7 days following vaccination AEs through 4 weeks after vaccination MAEs through 6 months after vaccination NDCMCs through 6 months after vaccination SAEs through 6 months after vaccination
Secondary immunogenicity	To describe the immune response elicited by tIRVs in participants 18 through 64 years of age	
 HAI titers for the 2023-2024 northern hemisphere seasonal strains recommended by WHO for CCI influenza vaccines 	
In participants complying with the key protocol criteria (evaluable immunogenicity population [HAI CCI]):
 
 HAI GMTs at baseline and 4 weeks after vaccination HAI GMFRs from before vaccination to 4 weeks after vaccination The proportion of participants achieving HAI seroconversion^a for each strain at 4 weeks after vaccination The proportion of participants with HAI titers $\geq 1:40$ for each strain at baseline and 4 weeks after vaccination

Type	Objective	Endpoint	Estimand
CCI			

090177e1a0eba359\Approved\Approved On: 13-Jun-2024 14:08 (GMT)

Type	Objective	Endpoint	Estimand
CCI			

- a. Seroconversion is defined as an HAI titer $<1:10$ prior to vaccination and $\geq 1:40$ at the time point of interest, or an HAI titer $\geq 1:10$ prior to vaccination with at least a 4-fold rise at the time point of interest.

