2.3. Study Design

This is a Phase 2, randomized, observer-blinded (sponsor-unblinded) substudy to evaluate the safety, tolerability, and immunogenicity of 3 different formulations of tIRV (tIRV1 through tIRV3) encoding HA for the targeted seasonal influenza strains compared to QIV1 CCI and qIRV1 (encoding HA for 2 A and 2 B seasonal influenza strains) in healthy adults 18 through 64 years of age.

Up to approximately 450 participants 18 through 64 years of age will be enrolled and randomized to receive 1 dose of study intervention as shown in Table 2.

Blood samples of approximately 30 mL will be collected CCI prior to vaccination and at 4 weeks and 6 months after vaccination.

Local reaction and systemic event data will be collected in an e-diary during the 7-day follow-up period after vaccination. Participants are required to complete the e-diary every evening (06:00 PM to 11:59 PM) for the 7 days following vaccination (including the day of vaccination). If participants are unable to complete the e-diary as expected on a particular day, they are allowed to retrospectively complete the missed entry within up to 3 days following the date of the missed entry (extended 72-hour e-diary reporting window).

For participants with ongoing symptoms after Day 7, subsequent e-diary entries will be followed only to monitor the duration of symptoms until resolution. The end date for the prespecified local reaction and systemic event beyond Day 7 will also be recorded on the Summary of Reactogenicity CRF page.

All AEs will be collected from informed consent signing through 4 weeks following vaccination. A subset of AEs (NDCMCs, MAEs, and SAEs) will be collected from informed consent signing through 6 months after vaccination. In addition, AEs occurring up to 48 hours after blood draws will be collected.

Table 2. Number of Participants to Be Enrolled in Substudy A – Participants 18 Through 64 Years of Age

Study Intervention	Preformulated ^a	Influenza Strains	CCI	Total modRNA Dose	Number of Participants
QIV1	Yes	2023-2024 northern hemisphere seasonal strains recommended by WHO for CCI influenza vaccines		N/A	90
tIRV1	Yes	A/H1N1		CCI	90
		A/H3N2			
		B/Victoria			

Table 2. Number of Participants to Be Enrolled in Substudy A – Participants 18 Through 64 Years of Age

Study Intervention	Preformulated ^a	Influenza Strains	CCI	Total modRNA Dose	Number of Participants
tIRV2	No	A/H1N1	CCI	CCI	90
		A/H3N2			
		B/Victoria			
tIRV3	No	A/H1N1			90
		A/H3N2			
		B/Victoria			

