5.2. General Methods

CI for all endpoints in the statistical analysis will be presented as 2-sided at the 95% level unless specified otherwise.

The safety analyses are based on the safety population. Participants will be summarized by vaccine group according to the study interventions they actually received. Completely missing reactogenicity e-diary data will not be imputed; missing AE dates will be handled according to the Pfizer safety rules.

For the immunogenicity endpoints, the main analysis will be based on the evaluable immunogenicity population. Antibody titers below the LLOQ, denoted as BLQ, will be set to $0.5 \times \text{LLOQ}$ for GMT analysis. No other missing assay data will be imputed in the analyses. All immunogenicity analyses will be performed after the imputation of the antibody titers that are below the LLOQ.

An additional analysis may be performed based on the mITT immunogenicity populations if there is a large enough difference ($>10\%$) in sample size between the mITT immunogenicity population and the evaluable immunogenicity population. Participants will be summarized according to the vaccine group to which they were randomized. Missing serology data will not be imputed.

No formal multiplicity adjustments will be applied for the analyses in multiple endpoints or for multiple looks of the same endpoint due to the descriptive nature of this substudy.

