5.2.2.2. Geometric Mean Fold Rises

GMFRs are defined as the geometric mean of the fold rise in the assay results from before to a specified time point after vaccination. GMFRs are limited to participants with nonmissing values at both time points.

GMFRs will be calculated as the mean difference of logarithmically transformed assay results (later time point minus earlier time point) and exponentiating the mean difference. The associated 2-sided 95% CIs will be obtained by constructing CIs using the Student t distribution for the mean difference on the logarithm scale and exponentiating the confidence limits.

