5.2.2.3. Geometric Mean Ratios

The GMR will be calculated as the mean of the difference of logarithmically transformed assay results and exponentiating the mean. Two-sided CIs will be obtained by calculating CIs using the Student t distribution for the mean difference of the logarithmically transformed assay results and exponentiating the confidence limits.

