6.2.1.1. Main Analysis

- Estimand strategy: Hypothetical approach ([Section 2.2.2](#)).
- Analysis set: Evaluable immunogenicity population (HAI CCI) ([Section 4](#)).
- Analysis methodology: Descriptive summary statistics ([Section 5.2.1](#) and [Section 5.2.2](#)).
- Analysis timing: Day 1 prior to study intervention administration (HAI GMTs, HAI titers $\geq 1:40$) and at 4 weeks after vaccination.
- Intercurrent events and missing data: All data collected after or at intercurrent events will be excluded ([Section 2.2.2](#)). Antibody titers below the LLOQ, denoted as BLQ, or below the LOD will be set to $0.5 \times \text{LLOQ}$ for analysis ([Section 5.3.2](#)). Missing data will not be imputed. Immunogenicity data that are confirmed as not valid will not be used for analysis.

Reporting results:

- Descriptive statistics, including the sample size (n), HAI GMTs, HAI GMFRs, and 95% CIs for the HAI GMTs and HAI GMFRs, will be presented for each strain and each study intervention group ([Section 5.2.2](#)).

- Descriptive statistics, ie, HAI GMRs of each tIRV (tIRV1, tIRV2 and tIRV3) group compared with each control group (QIV1, qIRV1) at 4 weeks after vaccination, and the 95% CIs for the HAI GMRs, will be presented for each strain ([Section 5.2.2](#)).
- The proportion of participants achieving HAI seroconversion for each strain at 4 weeks after vaccination, and the associated 2-sided Clopper-Pearson 95% CIs, will be provided by study intervention group.
- The proportion of participants with HAI titers $\geq 1:40$ for each strain before vaccination and at 4 weeks after vaccination, and the associated 2-sided Clopper-Pearson 95% CIs, will be provided by study intervention group.
- Empirical RCDCs will be plotted by study intervention group.
- HAI GMTs for each strain, and the associated 95% CIs, will be plotted by study intervention group.
- HAI seroconversion rate for each strain, along with the associated 95% CIs, may be plotted by study intervention group.

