6.2.1.1. Main Analysis

- Estimand strategy: Hypothetical approach ([Section 2.2.2](#)).
- Analysis set: Evaluable immunogenicity population (HAI CCI) ([Section 4](#)).
- Analysis methodology: Descriptive summary statistics ([Section 5.2.1](#) and [Section 5.2.2](#)).
- Analysis timing: Day 1 prior to study intervention administration (HAI GMTs, HAI titers $\geq 1:40$) and at 4 weeks after vaccination.
- Intercurrent events and missing data: All data collected after or at intercurrent events will be excluded ([Section 2.2.2](#)). Antibody titers below the LLOQ, denoted as BLQ, or below the LOD will be set to $0.5 \times \text{LLOQ}$ for analysis ([Section 5.3.2](#)). Missing data will not be imputed. Immunogenicity data that are confirmed as not valid will not be used for analysis.

Reporting results:

- Descriptive statistics, including the sample size (n), HAI GMTs, HAI GMFRs, and 95% CIs for the HAI GMTs and HAI GMFRs, will be presented for each strain and each study intervention group ([Section 5.2.2](#)).

- Descriptive statistics, ie, HAI GMRs of each tIRV (tIRV2 and tIRV3) group compared with each control group (QIV2, QIV3, and qIRV2) at 4 weeks after vaccination, and the 95% CIs for the HAI GMRs, will be presented for each strain ([Section 5.2.2](#)).
- The proportion of participants achieving HAI seroconversion for each strain at 4 weeks after vaccination, and the associated 2-sided Clopper-Pearson 95% CIs, will be provided by study intervention group.
- The proportion of participants with HAI titers $\geq 1:40$ for each strain before vaccination and at 4 weeks after vaccination, and the associated 2-sided Clopper-Pearson 95% CIs, will be provided by study intervention group.
- Empirical RCDCs will be plotted by study intervention group.
- HAI GMTs for each strain, and the associated 95% CIs, will be plotted by study intervention group.
- HAI seroconversion rate for each strain, along with the associated 95% CIs, may be plotted by study intervention group.

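### The 4-week HAI geometric mean ratios in Substudies A and B are not adjusted for the pre-vaccination titre, which costs precision and leaves them exposed to baseline differences if groups open at different times

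*SAP*

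**What the plan says.** SAP section 5.2.2.3, identical for Substudies A and B, defines the ratio: "The GMR will be calculated as the mean of the difference of logarithmically transformed assay results and exponentiating the mean". The interval comes from the Student t distribution on the log scale. No covariate, model or group structure is named.

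Section 6.2.1.1 says where it is used. In Substudy A the SAP reports "HAI GMRs of each tIRV (tIRV1, tIRV2 and tIRV3) group compared with each control group (QIV1, qIRV1) at 4 weeks after vaccination"; in Substudy B, "HAI GMRs of each tIRV (tIRV2 and tIRV3) group compared with each control group (QIV2, QIV3, and qIRV2) at 4 weeks after vaccination". Both are by strain. The default interval is set in section 5.2: "CI for all endpoints in the statistical analysis will be presented as 2-sided at the 95% level unless specified otherwise".

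The baseline titre is available. Section 2.3 has blood drawn "prior to vaccination and at 4 weeks and 6 months after vaccination", and the secondary estimands in section 2.2 include "HAI GMTs at baseline and 4 weeks after vaccination". Baseline enters the by-group summaries: baseline GMT, baseline proportion at or above 1:40, GMFR and seroconversion. No readable analysis uses it in a comparison between groups.

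Protocol sections 10.11.4.1 and 10.12.4.1 allow study groups to be randomized at different times and require only two groups to be open together.

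**The concern.** The GMR is the only between-group immunogenicity contrast in the readable SAP. Using only the 4-week titres leaves in each arm's mean all the variation between participants that their pre-vaccination titre could explain. The intervals are then wider than necessary, and any baseline difference between two groups passes partly into the 4-week ratio.

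Under concurrent randomization such differences arise only by chance. If groups open at different times they can be systematic. Influenza vaccination within 180 days is an exclusion (Protocol 10.11.5.2 and 10.12.5.2), while earlier vaccination is allowed. As enrolment moves later, more recipients of the 2023-2024 vaccine become eligible, and HAI is measured against those same strains. Later groups could therefore start from different titres. Nothing in the readable text requires a tIRV and its control to be open together, or limits the GMR to participants randomized over the same period.

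The substudies are meant to inform the choice of formulation (Protocol 10.11.2.1 and 10.12.2.1), with the influenza B response as the stated motive, so accurate between-group estimates have value even in a descriptive study.

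**Working it through.** **The plan's own figure.** The documents give no precision or power for the GMR. The only sample-size figure for Substudy A is Table 6 of the protocol, the chance of seeing at least one adverse event with 90 participants, 1 − (1 − p)^90. For p = 0.5%, 1%, 2%, 5% and 7% this gives 36.31%, 59.53%, 83.77%, 99.01% and 99.85%. The table states 36.3%, 59.5%, 83.8%, 99.0% and 99.9%, so it reproduces.

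**Inputs from the documents.** n = 90 per group ("Approximately 90 participants will be enrolled in each vaccine group", Protocol 10.11.9.5; Substudy B plans the same number), and 95% two-sided intervals.

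**Assumptions, not in the documents.** SD of log10 titre 0.4 to 0.7, equal in both groups and at both times; baseline to 4-week correlation r of 0.3 to 0.7; no dropout, with 10% non-evaluable (81 per group) as a check.

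**Formulas, on the log10 scale.**

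- Unadjusted half-width: t(0.975, 2n − 2) × SD × √(2/n).
- Adjusted half-width: t(0.975, 2n − 3) × SD × √[(1 − r²) × (2/n) × (1 + 1/(2n − 4))].
- Equivalent unadjusted sample size: n/(1 − r²).

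Example with SD 0.6: the unadjusted half-width is 1.973 × 0.6 × √(2/90) = 0.176, and 10^0.176 is a multiply-or-divide factor of 1.50 around the GMR. At r = 0.5 the adjusted half-width is 0.869 times that, a factor of 1.42.

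**CI factor around the GMR, n = 90 per group**

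| SD | Unadjusted | r = 0.3 | r = 0.5 | r = 0.6 | r = 0.7 |
|---|---|---|---|---|---|
| 0.4 | 1.311 | 1.296 | 1.265 | 1.243 | 1.214 |
| 0.5 | 1.403 | 1.383 | 1.342 | 1.312 | 1.275 |
| 0.6 | 1.501 | 1.475 | 1.423 | 1.386 | 1.338 |
| 0.7 | 1.607 | 1.574 | 1.510 | 1.463 | 1.404 |
| Log-scale narrowing | – | 4.3% | 13.1% | 19.8% | 28.4% |
| Equivalent n per group | 90 | 99 | 120 | 141 | 176 |

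The percentage narrowing does not depend on the SD. With 81 per group it is essentially unchanged. At r = 0 adjustment widens the interval by 0.3%. A simulation (2,000 trials at each of r = 0.3, 0.5 and 0.7, SD 0.6) gave 4.3%, 13.1% and 28.4%.

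**Carry-over of a baseline difference.** A baseline log difference d moves the unadjusted 4-week log GMR by r × d. With SD 0.6, one standard error of the baseline difference is 0.6 × √(2/90) = 0.089, a baseline ratio of 1.229. It shifts the 4-week GMR by a factor of 1.064, 1.108 or 1.155 at r = 0.3, 0.5 or 0.7. A difference of 1.96 standard errors (baseline ratio 1.497) shifts it by 1.129, 1.224 or 1.327.

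**The case against.** The strongest reply is that this is one descriptive row in a study with no hypothesis test, margin or decision rule (SAP 5.1). The GMR is not part of the secondary estimand summary (SAP 2.2.2), and no sample size rests on it. Under concurrent randomization the unadjusted GMR is unbiased, and its two-sample t interval already allows for chance imbalance. The gain depends wholly on a correlation the documents do not give, and at r = 0.3 it would hardly change a reading. All of this stands. It makes the point one of efficiency and robustness.

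A reader might infer more, and the documents do not support it:

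- *Baseline is ignored.* It is not: GMFR and seroconversion are responses relative to baseline, and baseline GMTs appear beside the GMR. Comparing GMFRs by eye is no substitute, however. With equal SDs the relative variance of a fold-rise contrast is 2(1 − r), or 1.4, 1.0 and 0.6 at r = 0.3, 0.5 and 0.7, against 0.91, 0.75 and 0.51 for ANCOVA.
- *Age is unused.* SAP A section 6.5 repeats the main immunogenicity analysis in the 18–49 and 50–64 age groups.
- *No other between-group comparison is planned.* Protocol 9.3.1.1 names Miettinen-Nurminen intervals for binary differences, and part of the SAP is redacted.
- *The formula would give a wrong result.* The wording resembles the paired GMFR definition ("later time point minus earlier time point"), but section 6.2.1.1 makes clear that independent groups are meant. Different participants cannot be paired, so this is a drafting slip.
- *Selection of a formulation rests on the GMR.* The protocol says the substudies inform that choice; it does not tie it to this statistic.

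**Conclusion.** The point holds as a missed, nearly free improvement in Substudies A and B. The planned GMR is valid under concurrent randomization. Adjustment for baseline titre would narrow its log-scale interval by about 4% at r = 0.3 and 28% at r = 0.7, equivalent to about 99 to 176 participants per group in place of 90. The percentage rests on the assumed correlation alone; the CI factors also need the assumed SD. Adjustment would also remove the carry-over of chance baseline differences. With staggered opening of groups it would reduce the resulting bias but not eliminate it, because calendar-time or site-mix differences need not act through the baseline titre.

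**What to change.** In SAP sections 5.2.2.3 and 6.2.1.1, for both A and B:

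- Estimate each GMR by ANCOVA on log 4-week titre, with vaccine group and log baseline titre for the same strain as terms, plus age if wanted. Report exponentiated adjusted mean differences with 95% CIs.
- State which baseline value enters the model. Section 5.3.2 has different rules for GMT and for fold rise, both for values below the LLOQ and for multiple assay batches. Use the baseline from the same batch as the 4-week result, with values below the LLOQ set to 0.5 × LLOQ.
- Keep the unadjusted GMR as a supplementary row, reworded as the exponentiated difference between two independent group means of log titre with a two-sample t interval.

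The cost is SAP wording and one extra model per strain; no new data are needed. Participants without a baseline titre drop out of the adjusted model, as they already do from the GMFR.

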5.2.2.4. Reverse Cumulative Distribution Curves

Empirical RCDCs will plot proportions of participants with values equal to or exceeding a specified assay value versus the indicated assay value, for all observed assay values. Data points will be joined by a step function with the line first going down and then to the right to the next assay value.

5.3. Methods to Manage Missing Data

5.3.1. Safety Data

Standard algorithms for handling missing AE dates, AE severity, laboratory test values, and ECG values will be applied according to the Pfizer safety rules. Missing data handling rules for safety data are described in detail in the corresponding endpoint sections.

5.3.1.1. Reactogenicity Data

Completely missing reactogenicity e-diary data (no data from both the 7-day e-diary and the Participant Reported Reactogenicity CRF page) will not be imputed. For derived variables based on reactogenicity data, if any day of the 7-day e-diary data are available, the “any day (Day 1 through Day 7)” data will be considered nonmissing.

The reactogenicity data are collected through the e-diary, which does not allow participants to skip the question. Therefore, for a specific day, as long as the e-diary data are transferred for that day, all of the reactogenicity data for the participant on that day are nonmissing.

For the “I do not recall” data in the e-diary, it will be imputed as “no” as described in [Table 3](#) and [Table 4 in Section 3.1.1](#). No missing reactogenicity data will be imputed other than what is described in [Section 3.1.1](#) and [Section 3.1.2](#).

In summary, for any participant with all 7 days of the e-diary missing (no data from both the 7-day e-diary collection period and the Participant Reported Reactogenicity CRF page), this will not be included in the analysis (ie, assuming MCAR). If only 1 to 6 days of reactogenicity data are available, the reactogenicity data for the missing day(s) are considered as answering “no” for all reactions. This is based on the common assumption that no reports mean no events. See [Table 3](#) and [Table 4](#) for the derivation algorithms.

5.3.2. Immunogenicity Data

Any assay results above the LLOQ are considered accurate, and their quantitated values will be reported. Antibody titers below the LLOQ, denoted as BLQ, or below the LOD will be set to $0.5 \times \text{LLOQ}$ for GMT analysis. No other missing assay data will be imputed in the analyses. All immunogenicity analyses will be performed after the imputation of the antibody concentrations or antibody titers that are below the LLOQ.

When calculating a fold rise, the assay results will be converted to $0.5 \times \text{LLOQ}$ if assay results are $< \text{LLOQ}$, except when the prevaccination assay result is $< \text{LLOQ}$ while the postvaccination result is $\geq \text{LLOQ}$, in which case the prevaccination value will be set to LLOQ. If both the numerator and denominator are $< \text{LLOQ}$, then both will be converted in the same way.

If there are multiple batch assay results at baseline, the GMT will be calculated from the mean of the baseline assay results. GMFR and seroconversion will be calculated using paired baseline and postbaseline assay results from the same batch of assay data. If there is more than 1 assay value at baseline due to multiple assay result batches, the titer criterion $\geq 1:40$ will be met if any of the assay values are $\geq 1:40$.

Values for sera that are insufficient (QNS), IND results, or values recorded as “not done” will be set to “missing.” Additionally, any time point with no blood draws will not be included in the analysis. No imputation will be done for these missing values, as MCAR is assumed for immunogenicity data.

LLOQ results for each assay used in this study will be included in the analysis specification once they are available.

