9.3.1. General Considerations

CIIs for all endpoints in the statistical analysis will be presented as 2-sided at the 95% level unless specified otherwise.

The safety analyses are based on the safety population. Participants will be summarized by vaccine group according to the study interventions they actually received. Completely missing reactogenicity e-diary data will not be imputed; missing AE dates will be handled according to the Pfizer safety rules.

For all the immunogenicity endpoints (HAIs CCI), the analysis will be based on the evaluable immunogenicity population. Antibody titers below the LLOQ or denoted as BLQ will be set to  $0.5 \times \text{LLOQ}$  for immunogenicity analysis. All immunogenicity analyses will be performed after the imputation of the antibody concentrations or antibody titers that are below the LLOQ.

An additional analysis may be performed based on the mITT immunogenicity population (HAIs CCI) if there is a large enough difference in sample size between the mITT immunogenicity population and the evaluable immunogenicity population. Participants will be summarized according to the vaccine group to which they were randomized. Missing serology data will not be imputed.

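### Two separate baseline-titre rules in SAP 5.3.2 (Substudies A and B): an outcome-dependent substitution that lowers the HAI fold rise, and a maximum over batches for baseline titres ≥1:40

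*SAP*

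**What the plan says.** **Values below the LLOQ.** Protocol 9.3.1 gives a single rule, 0.5×LLOQ for immunogenicity analysis, and adds: "All immunogenicity analyses will be performed after the imputation of the antibody concentrations or antibody titers that are below the LLOQ". The protocol's fold-rise definition (9.3.1.2.2) contains no exception.

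SAP 5.3.2, identical for Substudies A and B, starts the same way ("Antibody titers below the LLOQ, denoted as BLQ, or below the LOD will be set to" 0.5×LLOQ) but limits this to GMT analysis. For fold rise it also uses 0.5×LLOQ, unless the prevaccination result is below the LLOQ and the postvaccination result is not, "in which case the prevaccination value will be set to LLOQ". When both results are below the LLOQ, both are converted alike, so the fold rise is 1.

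SAP 6.2.1.1, which reports GMTs and GMFRs together, states 0.5×LLOQ for analysis and refers back to 5.3.2. SAP 2.1, which lists modifications to the protocol analysis, says there are none.

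**Several baseline batches.** SAP 5.3.2 has a different rule for each summary:
- GMT: "the GMT will be calculated from the mean of the baseline assay results" (arithmetic or geometric is not stated).
- Fold rise and seroconversion: "GMFR and seroconversion will be calculated using paired baseline and postbaseline assay results from the same batch of assay data".
- Titre ≥1:40: the criterion "will be met if any of the assay values are" at or above 1:40. The rule is for baseline only.

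The LLOQ is not stated; it is deferred to the analysis specification.

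**The concern.** The value given to an unquantifiable baseline depends on what happens after vaccination. It is LLOQ if the participant later becomes quantifiable and 0.5×LLOQ if not. The rule is also asymmetric. A move from below the LLOQ up to the LLOQ counts as no change, while the reverse move counts as a halving. The reported GMFR is therefore lower than the protocol's rule would give. It is lowered more in any arm that brings more participants above the LLOQ, and SAP 2.1 does not tell the reader that the rule has changed.

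The batch rule is a different matter. Taking the best of several baseline readings can only push the baseline ≥1:40 proportion up. It is tabulated beside a 4-week proportion for which no such rule is given.

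Both summaries are secondary and descriptive. Substudies A and B are, however, meant to inform the choice of formulation where B-strain responses have been attenuated, so readers are likely to look at GMFR across arms.

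**Working it through.** The documents give no GMFR, LLOQ, baseline distribution or assay variability, so there is no planned figure to reproduce. The first relation below is exact. The sizes rest on assumptions, marked as such.

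**1. Fold rise.** Take a participant with baseline below and 4-week titre at or above the LLOQ:
- baseline 0.5×LLOQ: log2 fold rise = log2(post) − log2(LLOQ) + 1
- baseline LLOQ: log2 fold rise = log2(post) − log2(LLOQ)

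The difference is exactly 1. All other participants are treated identically. With f the share of affected participants, the mean log2 fold rise falls by f, so

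GMFR(SAP) = GMFR(0.5×LLOQ throughout) × 2^(-f).

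| f (assumed) | factor | a GMFR of 4.00 is reported as |
|---|---|---|
| 10% | 0.933 | 3.73 |
| 20% | 0.871 | 3.48 |
| 30% | 0.812 | 3.25 |
| 50% | 0.707 | 2.83 |

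A simulation with an assumed LLOQ of 1:10 and two-fold dilutions gave f = 0.363. The GMFR was 4.39 under 0.5×LLOQ and 3.41 under the SAP rule, a ratio of 0.778 = 2^(-0.363). The 4-week GMT divided by the baseline GMT in the same participants stayed at 4.39.

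**2. Asymmetry.** Suppose there is no true change and a share q crosses the LLOQ in each direction, with mirror-image fold changes. Under 0.5×LLOQ these cancel and the GMFR is 1. Under the SAP rule each upward crosser loses one log2 unit, so the GMFR is 2^(-q), for example 0.933 at q = 10%.

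**3. Between arms.** For assumed f of 36% and 24%, the ratio of the two GMFRs is multiplied by 2^(-(0.36 − 0.24)) = 2^(-0.12) = 0.92. The GMR planned in SAP 6.2.1.1 uses 4-week titres only, so it does not change.

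**4. Seroconversion.** The definition is <1:10 to ≥1:40, or ≥1:10 with at least a 4-fold rise.
- LLOQ 1:10: a below-LLOQ baseline is 5 (first limb, post ≥40 needed) or 10 (second limb, 4×10 = 40 needed). The result is the same.
- LLOQ 1:20: <20 to 40 is 40/10 = 4-fold with 0.5×LLOQ, which counts, and 40/20 = 2-fold with LLOQ, which does not.

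**5. Baseline ≥1:40 with repeat assays.** If one reading reaches 1:40 with probability p, at least one of k independent readings does so with probability 1 − (1 − p)^k. For p = 0.3 this is 0.51 with two readings and 0.66 with three. For a population (assumed median 1:20, SD 1.8 log2, everyone assayed twice):

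| assay SD (log2, assumed) | one reading | any of two | geometric mean of two |
|---|---|---|---|
| 0.25 | 29.2% | 31.9% | 26.5% |
| 0.5 | 29.6% | 34.8% | 25.1% |
| 1.0 | 31.4% | 41.3% | 25.9% |

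The any-reading rule adds 2.7, 5.2 and 9.9 points in these rows. The excess shrinks in proportion to the share actually assayed more than once, and is zero if nobody is. The geometric mean errs the other way in this set-up, because a 20 and 40 pair averages to √800 = 28.3.

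**The case against.** A below-LLOQ baseline is unknown, and 0.5×LLOQ is a convention, not the truth. Setting it to LLOQ takes its upper bound, makes each affected fold rise a lower bound, and stops a step from just below the LLOQ to the LLOQ from counting as two-fold. That stands: the GMFR is lower relative to the protocol's rule, not shown to be lower than a true value. It does not explain why the convention should depend on the outcome or act in one direction only.

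The SAP may modify the protocol without an amendment unless a primary endpoint is materially changed, and 6.2.1.1 refers back to 5.3.2, where the exception can be found. This also stands. The fault is a missing declaration and loosely aligned wording, not a forbidden change.

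A reader might infer more than the documents support:
- *That the rules contradict one another.* They do not. The LLOQ rules concern censored values and the batch rules concern repeat assays. Each serves its own summary and each can be programmed.
- *That the planned comparison between vaccines is biased.* The planned HAI comparison is the 4-week GMR, which uses no baseline, and the visible text plans no ratio of GMFRs. Comparing GMFRs across arms would be informal.
- *That only true responders are penalised.* The trigger is any postvaccination result at or above the LLOQ, which is well short of seroconversion.
- *That re-assay differs between arms.* Protocol 8.2.2 keeps participant, visit and cohort from the laboratory analyst, and nothing in the documents points to an imbalance.

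**Conclusion.** The point holds as two limited defects in descriptive secondary summaries of Substudies A and B.

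First, the fold-rise exception is outcome-dependent and asymmetric, departs from protocol 9.3.1, and is not declared in SAP 2.1. Relative to 0.5×LLOQ it multiplies the GMFR by exactly 2^(-f): 0.93 to 0.81 for an assumed f of 10% to 30%, and lower still in arms with larger f. The relation is certain; the value of f is not in the documents. The 4-week GMR is untouched. Seroconversion is also untouched if the LLOQ is 1:10, but could change if it is higher.

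Second, the any-reading rule can only raise baseline ≥1:40 and has no 4-week counterpart. It would be wrong to infer that baseline seroprotection is overstated in this trial as a matter of fact. That happens only where baseline was assayed in more than one batch, and the documents do not say whether or how often this occurs. The simulated 2.7 to 9.9 points assume that everyone is assayed twice.

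Both are worth correcting before analysis, since each can be settled in the SAP text. Neither threatens the primary safety objective.

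**What to change.** In SAP 5.3.2 for Substudies A and B:

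- **GMFR.** Use 0.5×LLOQ for every below-LLOQ titre, before and after vaccination, as in the protocol. Show the LLOQ version as a labelled sensitivity analysis. If the LLOQ version is kept as the main analysis, declare it in SAP 2.1, align 6.2.1.1 with it, and show the 0.5×LLOQ GMFR beside it.
- **LLOQ and seroconversion.** State the LLOQ. State that the 4-fold limb applies only to baselines ≥1:10 and, should the LLOQ exceed 1:10, how a below-LLOQ baseline is classified. Changing the substitution could then change seroconversion results.
- **Baseline ≥1:40.** Replace the any-reading rule with one baseline value per participant. This can be the reading from the batch paired with the 4-week sample, already used for GMFR and seroconversion, or the geometric mean of the readings. If the mean is chosen, say that it is geometric and use it for the GMT as well. The paired reading discards data but treats baseline and 4 weeks alike; the geometric mean keeps all readings but, with two-fold dilutions, can sit below a single reading, as in step 5 of the check.

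The cost is SAP wording and one extra table; no new data are needed. The downside is that the GMFR will be somewhat higher than in any earlier report that used the LLOQ rule, by a factor of 2^f. The sensitivity analysis keeps that link.
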